### 7.3. Study Oversight

The study will utilize a Steering Committee (SC). The SC is responsible for the scientific content of the study and provides input for the execution. Members of the SC may be study site investigators. The purpose of the SC is to provide unbiased opinions and expertise to the clinical study design and process. The SC will support the execution of the REVAMP clinical study and provide guidance, feedback and direction to the clinical study. The SC is comprised of the members as indicated below.

## **8. Product Description**

### **8.1. General**

All Medtronic implantable pacemakers and associated programmer and monitoring equipment must be market-released. The Medtronic pacemakers must offer the Sleep Function feature. The pacing parameter Lower Rate will be programmed to 100bpm, and the Sleep Function will be used to lower the Sleep Rate to the pre-study lower rate (50-70 bpm) during 19 hours of the day. The Sleep Function will be programmed to deliver the Sleep Rate between 5a.m. and 11:30pm, using a Bed Time of 5a.m. and a Wake Time of 11:30pm. Subjects will receive 5 hours of elevated night pacing at 100bpm and 1 hour of a transition rate between 100bpm and the Sleep Rate. See Figure 2.

### **8.2. Intended Population**

[figure not shown]
All subjects in this investigation have received a Medtronic dual chamber pacemaker for approved indications. HFpEF subjects who have a small to normal LV volume and evidence of LV hypertrophy and/or increased LV wall thickness will be selected for this study.

### **8.3. Study Components**

- All Medtronic dual chamber pacemakers that have the Sleep Function
- Medtronic market-released programmers
- Compatible market-released leads
- Finger Pulse Oximeter Monitor (will be provided to the site)
- Echocardiography machine capable of recording and exporting echo data in digital format
- Access to dry ice to ship blood samples
- Computer with high speed internet access using a web browser compatible with the electronic data management system for electronic database entry

### **8.4. Product Use**

The Sleep function in all Medtronic market-released devices was designed to temporarily substitute the programmed Lower Rate with a slower pacing rate (Sleep Rate) during the time of day that the patient normally sleeps. This feature can be programmed to lower the rate to the Sleep Rate at "Bed time" and to increase the rate back to the Lower Rate at "Wake time". The design intent of this feature was that the slower Sleep Rate can be programmed to occur during any window in the 24 hour clock; the difference between Bed Time and Wake Time must be a minimum of 2 hours. The REVAMP study proposes to use the lower Sleep Rate for 18 hours during the day, in order to elevate the Lower Rate to 100bpm and pace the atrium at an elevated rate at night. For the REVAMP study, we specify the Lower Rate programmed at 100bpm, with the Sleep Rate programmed to the pre-study value of the Lower Rate (e.g. 60bpm).

**Figure 2: Sleep Function On During the Day**

The Sleep Function will be programmed to deliver the Sleep Rate between 5a.m. and 11:30pm, using a Bed Time of 5a.m. and a Wake Time of 11:30pm.

The Sleep Function was designed to operate in conjunction with Rate Responsive pacing; however, the Rate Profile Optimization feature that automatically optimizes was not developed with 5 hours of 100bpm imposed on patients. Therefore, Rate Profile Optimization will be turned OFF while the Sleep Function is programmed ON.

The Sleep Function is suspended following any parameter programming operations. If the Sleep Function is suspended, the pacing rate will immediately return to the programmed Lower Rate (100bpm per this protocol) until the next Bed Time is reached. At the initial programming visit of this protocol, subjects will be evaluated for whether they are symptomatic at a Lower Rate of 100bpm. Subjects will leave the Baseline visit experiencing a Lower pacing rate of 100 bpm until 5am the next morning, when Bed Time for the Sleep Function is reached. After the elevated pacing has been turned ON, any telemetry activation, such as programming, magnet application or CareLink transmission will suspend the Sleep Function and the pacemaker will immediately return to the Lower Rate of 100 bpm until 5am.

If a pacemaker reaches Estimated Replacement Indicator (ERI), the device will automatically turn OFF the Sleep Function and reprogram the pacemaker to VVI 65 mode.

## 8.5. Product Receipt and Tracking

All product is market released and therefore does not need to be tracked.

# 9. Selection of Subjects

## 9.1. Study Population

This study will enroll patients who have a Medtronic dual chamber pacemaker system with the Sleep function per local guidelines and who meet all of the specific study inclusion criteria and none of the exclusion criteria.

## 9.2. Subject Enrollment

In order for subjects to be considered for enrollment, they must meet all of the inclusion criteria and none of the exclusion criteria. Notification of site activation from Medtronic, and approval from the IRB of the REVAMP Clinical Investigation Plan (CIP), Informed Consent Form (IC Form), Authorization to Use and Disclose Personal Health Information/Research Authorization/other privacy language (data protection authorization) as required by law, and any other applicable documents must be obtained prior to enrolling subjects in the study.

## 9.3. Inclusion Criteria

Subjects must meet all of the following inclusion criteria to be eligible to participate in the study:

INC 1: Subject has had a market released dual chamber Medtronic Pacemaker with a Sleep function for at least 3 months

INC 2: Subject is stable on current medications

INC 3: Subject has dyspnea with exertion or diagnosed as NYHA Class II or III heart failure.

INC 4: Subject has had a prior Echo in past 6 months with: EF  $\geq$  50% and Diastolic volume  $\leq$ 80 ml/m^2

INC 5: Subject has evidence of hypertrophy (indexed to body surface area: men 115 g/m^2, women 95 g/m^2 or indexed to height: men 49.2 g/m2.7, women 46.7 g/m2.7) or Relative Wall thickness  $>$ 0.42, or Wall Thickness  $\geq$ 1.2cm (posterior wall)

INC 6: Subject is willing to sign and date the study Informed Consent Form (IC Form) and Authorization to Use and Disclose Personal Health Information/Research Authorization/other privacy language (data protection authorization) as required by law

INC 7: Subject is 18 years of age or older, or of legal age to give informed consent per local law

INC 8: Subject is expected to remain available for follow-up visits

## 9.4. Exclusion Criteria

Subjects must not meet any of the following exclusion criteria to be eligible to participate in the study:

EXC 1: Subject has permanent AF or AF noted on baseline interrogation rhythm strip

EXC 2: Subject has uncontrolled BP; (systolic pressure needs to be  $>$ 100mmHg and  $<$ 160mmHg on medications)

EXC 3: Subject has severe stenosis of the aortic or mitral valve, defined as a valve area less than or equal to 1.0 cm^2 or subject has severe regurgitation of the aortic or mitral valve.

EXC 4: Subject has symptomatic COPD requiring oxygen

EXC 5: Subject's Pacemaker has less than 6 months of Pacemaker battery life

EXC 6: Subject had an aortic valve replacement (surgical or TAVR) procedure less than 9 months prior to enrollment.

EXC 7: Subject's programmed upper rate limit is less than 100 bpm because of concerns of elevated pacing

EXC 8: Subject is unable or unwilling to perform the 6 Minute Walk Test at all scheduled study visits

EXC 9: Subject is currently enrolled or planning to enroll in a potentially confounding trial during the course of the study (co-enrollment in concurrent studies is only allowed when documented pre-approval is obtained from the Medtronic study manager)

EXC 10: Subject is pregnant

EXC 11: Subject meets any exclusion criteria required by local law

EXC 12: Subject's life expectancy is less than 12 weeks

EXC 13: Subject with medical condition that precludes the patient from participation in the opinion of the investigator

EXC 14: Subject has known coronary disease with Class II angina

## 9.5. Minimization of Bias

Selection of subjects, treatment of subjects, and evaluation of study data are potential sources of bias. Methods incorporated in the study design to minimize potential bias include (but are not limited to):

- Subjects will be evaluated at Baseline to confirm eligibility for enrollment with defined inclusion/exclusion criteria prior to randomization
- Subjects will be randomly assigned to their treatment assignment
- Subject demographics and medical history will be collected at Baseline and differences that may affect endpoints will be identified
- Subjects will be blinded to their randomization assignment
- Data collection requirements and study procedures will be standardized across all sites
- All study site personnel and Medtronic personnel will be trained on their respective aspects of the study using standardized training materials, and required to follow the CIP
- Monitoring visits will be conducted according to the study-specific monitoring plan.
- A single Echocardiography Core Lab will be used to analyze the echo data, and members of the core lab will be blinded to subject's randomization
- A single Blood Core Lab will be used to analyze the blood data
- Registration of the trial on ClinicalTrials.gov

In summary, potential sources of bias that may be encountered in this clinical study have been considered and minimized by careful study design.

---

## 10. Study Procedures

Prior to performing study related procedures, all sites must have IRB approval and documentation from Medtronic of site readiness.

Medtronic representatives may perform the following activities at the study sites during the study, if appropriately trained and under supervision of the Principal Investigator:

- Study training relevant and pertinent to the involvement of personnel conducting study activities and investigator responsibilities
- Technical support at all visits (e.g. programming of the pacemakers according to study requirements, performing device interrogations/save-to-media, etc.), but no CRF data entry shall be performed by Medtronic personnel
- Monitoring activities

At the request of the Principal Investigator or other authorized site personnel, Medtronic will use information from its device registration database to provide a study site a list of its patients whom the site had implanted with the Medtronic dual chamber pacemaker with Sleep Function, required by the inclusion criteria set out in Section 9.3. Study site, if permitted by its IRB, could further review the records of such patients to determine if they may be eligible to participate in the study.

### **10.1. Study Personnel Requirements**

All clinical investigators managing the subject's heart failure must be qualified practitioners and experienced in the diagnosis and treatment of subjects with heart failure.

The role of the principal investigator is to implement and manage the day-to-day conduct of the clinical investigation as well as ensure data integrity and the rights, safety and well-being of the subjects involved in the clinical investigation.

The principal investigator shall:

- Be qualified by education, training, and experience to assume responsibility for the proper conduct of the clinical investigation
- Be experienced in the field of application
- Disclose potential conflicts of interest that interfere with the conduct of the clinical investigation or interpretation of results

The principal investigator shall be able to demonstrate that the proposed investigational site:

- Has the required number of eligible subjects needed within the recruitment period
- Has a qualified investigational site team and adequate facilities available for the foreseen duration of the clinical investigation

Site personnel training and delegation will be completed prior to participation in this clinical study.

### **10.2. Role of the Sponsor Representative**

Sponsor representatives may provide support as required for the study under supervision of the PI, including:

- Provide study training relevant and pertinent to the involvement of personnel conducting study activities and Investigator responsibilities
- Technical support at all visits under the supervision of a study Investigator, but no data entry, shall be performed by Medtronic personnel or their representatives at sites
- Monitoring activities

### **10.3. Site Activation**

During the activation process (prior to subject enrollment), Medtronic will train site personnel on the CIP, relevant standards and regulations, obtaining informed consent, and on data collection and reporting tools. If new members join the study site team, they will receive training on the applicable clinical study requirements relevant to their role before contributing to the clinical study. For new members, local IRB notification requirements must be met, as well as Medtronic requirements.

A Clinical Trial Agreement (CTA) or Work Order (WO) shall be entered into effect by Medtronic, the participating investigation site and/or the principal clinical investigator at each investigational site as per local legal requirements, and returned, fully executed, to Medtronic prior to the commencement of any study activities. Financial aspects of conducting and reporting a study will be specified in the agreement. By signing and dating the agreement the investigation site indicates approval of the CIP.

Prior to performing study related activities, all sites must have IRB approval.

All local and regional regulatory requirements will be fulfilled prior to site activation and enrollment of subjects into the study. Each study site must have written documentation from Medtronic of site and investigator readiness before beginning any study-related activities. Requirements for activation may include, but are not limited to the following:

- Written documentation of IRB approval of the current version of the CIP, IC Form, Authorization to Use and Disclose Personal Health Information/Research Authorization/other privacy language (data protection authorization) as required by law, subject materials, and voting list (as required by local law)
- Fully executed CTA or WO on file with the sponsor
- Investigator Agreement
- Current Curriculum Vitae (CV)
- Financial Disclosure Agreement
- Documentation of delegated tasks
- Documentation of study site personnel training

Additional requirements imposed by the IRB shall be followed, if applicable.

Medtronic will provide each study site with documentation of study site/investigator readiness; this letter must be received prior to subject enrollment.

#### **10.4. Equipment Requirements**

The following equipment must be available at each site to support study activities:

- Medtronic market-released programmers
- Echocardiography machine capable of recording and exporting echo data in digital format
- Access to dry ice for shipment of blood samples
- Computer with high speed internet access using a web browser compatible with the electronic data management system for electronic database entry

The maintenance and calibration of the programmers used for this study will be assessed outside of this clinical study. Sites are responsible for maintaining and calibrating non-programmer equipment used in the course of this study in accordance with established site practice. Records should be kept and able to be provided upon request by the Sponsor or regulatory agency.

#### **10.5. Schedule of Events**

Clinical data is collected at designated time points throughout the study as indicated in Table 4 below. Data will be collected using eCRFs, an electronic data management system for clinical studies. See Section 16.2. Data Management for more information. At the baseline, 4 week, 8 week, and 12 week visits subjects are to fill out the MN Living with Heart Failure Questionnaire and perform a 6 Minute Walk Test. At the same visits, an echocardiogram must be done, for which instructions are provided in an Echocardiography Handbook (provided under separate cover). A blood draw must also be done,

(instructions are provided under separate cover.) The device programming should occur after all other study procedures are complete, except for the final device interrogation and save-to-media. The EQ-5D-5L Questionnaire will only be collected at the Baseline and 8 week visits.

In addition to eCRF data, non-eCRF data will be collected to include device interrogation files/save-to-media and digital echo data.

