#### **6.1.2. Ancillary/Exploratory Objectives**

Adverse events, Minnesota Living With Heart Failure (MNLWHF) Questionnaire responses, EQ-5D-5L Questionnaire responses, 6 Minute Walk Test distances, resting heart rate, atrial fibrillation incidence, device-measured activity levels, echo measurements and blood samples will be collected at Baseline and follow-up visits as detailed in Section 10. Study Procedures. Adverse events will be collected as described in Section 12.1. Adverse Events and will be characterized to assess the overall safety and tolerability of the therapy, as described in Section 12.5.1. Adverse Event and Device Deficiency Classification. Changes in NT-proBNP and troponin concentrations from Baseline will also be used to assess patient safety. Early study patient withdrawals over the course of the study will be used to further assess therapy tolerability. Changes in quality of life, as assessed by the MN Living With Heart Failure and EQ-5D-5L, changes in 6 Minute Walk Test distance and change in activity levels will be compared from baseline to the various follow up time points to assess for therapy efficacy. Echo measurements and, optionally, peripheral blood concentrations of extracellular matrix biomarkers will be characterized and changes will be correlated with changes in the safety and efficacy assessments. End diastolic volume and mitral deceleration time could increase if the therapy works as hypothesized. If the quality of life, changes in 6 Minute Walk Test distance and/or activity levels improve, it will be of interest to see if the end diastolic volume and mitral deceleration time correlate with improvements. If the therapy works as hypothesized, other echo measurements, including left ventricular ejection fraction (LVEF), might also change over time, although the direction and magnitude of these effects are difficult to predict. Characterizing these effects will be an important goal of the feasibility study.

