### **6.2. Endpoints**

As part of the exploratory/ancillary safety, tolerability and efficacy effects described in Section 14.1. Endpoint Definitions, it will be of interest to characterize changes in collected measurements from Baseline to 4 weeks, compare changes in collected measurements at 4 weeks to 8 weeks in the subjects randomized to the elevated night pacing ON arm to subjects randomized to the elevated night pacing OFF arm and compare changes in collected measurements at 12 weeks to Baseline, 4 and 8 weeks to see whether any therapeutic improvements are sustained after the therapy is discontinued.

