### 10.11. Randomization (4 Week Follow-Up)

Subjects will be assigned to a group at random during the randomization visit. Randomization will occur at 4 weeks.

Subjects will be randomized in a 2:1 ratio to the Elevated Night Pacing ON or to the Elevated Night Pacing OFF group.

Sites will receive this randomization assignment from the randomization schedule, which is automatically populated on the eCRF.

Procedures to be performed and data to be collected at Randomization include:

- Physical Assessment (including weight, heart rate, symptoms, and blood pressure)
- Medications
- NYHA Class
- MN Living with Heart Failure Questionnaire
- 6 Minute Walk Test
- Echo\*
- Blood Draw\*\*
- Randomization assignment
- Device Interrogation/ (initial)
- Save-to-Media (initial)
- Device Programming, see Table 7: Programming Recommendations at 4 Week Follow-Up
- Device Interrogation (final) - this needs to be completed at the end of the visit after programming has been completed
- Save-to-Media (final)
- Adverse Events (report new/assess ongoing AEs), Study Deviations, System Modifications, Device Deficiencies, Crossovers (as they occur)

\*The echo must be sent to the Echo Core Laboratory for analysis, with a copy of the echo remaining at the site. Details of the Echo Core Laboratory, type of echo to be performed, and the review process will be provided in an Echocardiography Handbook (provided under separate cover).

\*\* The blood sample must be sent to the Blood Core Laboratory for analysis. Details of the blood core lab and the blood draw process will be provided under separate cover.

For any subject who has an abnormal NT-proBNP, troponin or LVEF measurement as defined in the Safety Assessment (Section 10.19. Assessment of Safety) and the investigator elects to discontinue elevated night pacing, a subsequent visit will be necessary for the elevated night pacing to be programmed OFF if the subject was randomized to the elevated pacing ON arm. The subject should continue to be followed through the 12 week visit.

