All subjects that completed 4 weeks of elevated night pacing. MNLWHF score at time of exit will be used for subjects that do not complete the full 4 weeks of participation in the study from week 4 to week 8.

**EQ-5D-5L Questionnaire – 8 weeks**Hypothesis

There is an improvement in quality of life from baseline after an 8 week period of elevated night pacing, as assessed by the EQ-5D-5L Questionnaire. This assumes the effect is the same whether or not elevated night pacing is turned off at week 4.

Analysis Methods

A paired comparison of the value at the end of the period compared to the value at the start of the period will be calculated. A one-sided paired t-test will be performed testing the hypothesis

$$H_0: \mu \leq 0$$

$$H_a: \mu > 0$$

Where  $\mu$  = difference in EQ-5D-5L score from baseline to week 8 visit

Determination of Subjects for Analysis

All subjects that completed 8 weeks of elevated night pacing. Subjects that were unable to tolerate or withdrew from the treatment during the first 4 weeks because of safety or other issues will not be included in this efficacy analysis. EQ-5D-5L score at time of exit will be used for subjects that do not complete the full 4 weeks of participation in the study from week 4 to week 8.

Hypothesis

There is more of an improvement in quality of life after an 8 week period of elevated night pacing than for a 4 week period of elevated night pacing followed by 4 weeks with the elevated night pacing programmed OFF after the initial 4 weeks period of elevated night pacing, as assessed by the EQ-5D-5L Questionnaire.

Analysis Methods

A paired comparison of the scores at the 8 week visit compared to the scored at the baseline visit will be calculated. A one-sided paired t-test will be performed testing the hypothesis

$$H_0: \mu_{ON} \leq \mu_{OFF}$$

$$H_a: \mu_{ON} > \mu_{OFF}$$

Where  $\mu_{ON}$  = difference in EQ-5D-5L score from baseline to week 8

Determination of Subjects for Analysis

All subjects that completed 8 weeks of elevated night pacing. Subjects that were unable to tolerate or withdrew from the treatment during the first 4 weeks because of safety or other issues will not be included in this efficacy analysis. EQ-5D-5L score at time of exit will be used for subjects that do not complete the full 4 weeks of participation in the study from week 4 to week 8.

**14.1.5. Ancillary Efficacy Endpoint - Mobility and Activity****6 Minute Walk Test Distance – 4 weeks**Hypothesis

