## Hypothesis

There is more of an improvement in quality of life after an 8 week period of elevated night pacing than for a 4 week period of elevated night pacing followed by 4 weeks with the elevated night pacing programmed OFF after the initial 4 weeks period of elevated night pacing, as assessed by the EQ-5D-5L questionnaire.

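### EQ-5D-5L at baseline and week 8 only leaves the OFF arm without an on-therapy score, the ON arm without a post-therapy score and both arms without a score at randomisation

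*Protocol*

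**What the plan says.** **Schedule.** Protocol section 10.5 states: "The EQ-5D-5L Questionnaire will only be collected at the Baseline and 8 week visits". SAP section 5.3 agrees, as do Protocol Table 4 and SAP Table 1, which mark no other visit for this form, including early exit. The other quality-of-life instrument is on a fuller schedule: "At the baseline, 4 week, 8 week, and 12 week visits subjects are to fill out the MN Living with Heart Failure Questionnaire". The walk test, echo and blood draw follow those same four visits.

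**Therapy and randomisation.** All subjects start elevated night pacing at baseline. Protocol section 10.11 says "Randomization will occur at 4 weeks" and "Subjects will be randomized in a 2:1 ratio to the Elevated Night Pacing ON or to the Elevated Night Pacing OFF group". Section 10.12.1 has everyone off by the end of the week 8 visit. Section 10.5 puts device programming after the other procedures, so an ON subject's week 8 questionnaire is completed while still on therapy.

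**Aims.** Protocol section 6.1.2 names EQ-5D-5L among the measures whose changes "will be compared from baseline to the various follow up time points to assess for therapy efficacy". Section 6.2 describes changes from baseline to week 4, week 4 to week 8 by arm, and week 12 against earlier visits, the last "to see whether any therapeutic improvements are sustained after the therapy is discontinued". Section 7.2 gives persistence of quality-of-life change as a reason for following subjects after therapy ends.

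**EQ-5D-5L tests.** Protocol section 14.1.4 and SAP section 7.9.4 specify two. The first is a one-sided single-group test of change from baseline to week 8, with the note: "This assumes the effect is the same whether or not elevated night pacing is turned off at week 4". The second compares ON with OFF on the same change; its hypothesis begins "There is more of an improvement in quality of life after an 8 week period of elevated night pacing than for a 4 week period", the comparator being 4 weeks on followed by 4 weeks off. Both tests define their analysis set as subjects who finished 8 weeks on the therapy.

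**The concern.** The design has three therapy states (before, during and after pacing) and a randomisation point at week 4. An instrument needs a score in each state, and preferably one at randomisation, to address the aims in sections 6.1.2, 6.2 and 7.2. EQ-5D-5L has one follow-up score per subject, and its therapy state depends on the arm: on therapy for ON, about 4 weeks after stopping for OFF.

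Two things are at stake. First, the only generic quality-of-life measure cannot say whether a week 8 difference between arms reflects added benefit from continuing or loss of benefit after stopping, and it cannot show whether any ON-arm benefit lasts. Second, to get a single-group result from week 8 scores, the plan assumes that the two therapy states are equivalent. That is the very question the second test asks.

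**Working it through.** The documents give no effect size, SD, power or alpha for EQ-5D-5L, so there is no plan figure to reproduce. The check is a grid of visits against therapy state, followed by illustrative arithmetic.

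**1. Grid (as scheduled)**

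| Instrument, arm | Baseline | Week 4 | Week 8 | Week 12 |
|---|---|---|---|---|
| EQ-5D-5L, ON | pre | none | on | none |
| EQ-5D-5L, OFF | pre | none | post | none |
| MNLWHF, ON | pre | on | on | post |
| MNLWHF, OFF | pre | on | post | post |

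EQ-5D-5L therefore has no on-therapy score in OFF, no post-therapy score in ON and no week 4 score in either arm. MNLWHF has all of them. Early stopping or crossover could create exceptions for individual subjects.

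**2. Mean of the single-group test if arms are pooled**

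Inputs: about 30 treated subjects (Protocol section 7) and 2:1 allocation, giving 20 ON and 10 OFF if all are randomised and assessed. Let r be the share of the ON effect still present in OFF at week 8.

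Pooled mean / ON effect = (20 + 10r) / 30

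- r = 0: 20/30 = 0.67
- r = 0.5: 25/30 = 0.83
- r = 1: 30/30 = 1.00

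The ON minus OFF difference tested next is (1 − r) times the ON effect. It is zero in the only case (r = 1) where the equal-effect assumption is true.

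**3. Power (illustrative)**

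Assumed, not in the documents: ON effect 0.5 SD of the change score, one-sided alpha 0.05. The small extra variance from mixing arms is ignored; at r = 0 it adds (2/3)(1/3)(0.5²) = 0.056 to a variance of 1. Paired test: noncentral t with n − 1 degrees of freedom and noncentrality d√n. Two-sample test: 28 degrees of freedom and noncentrality d/√(1/20 + 1/10).

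| r | Pooled d | d√30 | Pooled power, n = 30 | ON vs OFF power, 20:10 |
|---|---|---|---|---|
| 1 | 0.500 | 2.74 | 0.85 | 0.05 |
| 0.5 | 0.417 | 2.28 | 0.72 | 0.16 |
| 0 | 0.333 | 1.83 | 0.55 | 0.35 |

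The 20 ON subjects alone at week 8 give d√n = 0.5√20 = 2.24 and power 0.70. With r = 0, pooled power is 0.28 for an ON effect of 0.3 SD and 0.89 for 0.8 SD.

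**4. What a week 4 score would add**

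For a single-group baseline-to-week-4 test in all 30, power depends on how much of the effect is present by then:

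- all of it (0.5 SD): 0.85
- three quarters (0.375 SD): 0.64
- half (0.25 SD): 0.38

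For ON versus OFF, assume equal variances and a common between-visit correlation ρ. With unit variance, the baseline-to-8 change has variance 2(1 − ρ), an analysis adjusted for baseline has 1 − ρ², and one adjusted for baseline and week 4 has 1 − 2ρ²/(1 + ρ).

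- ρ = 0.5: 1.00, 0.75, 0.67
- ρ = 0.8: 0.40, 0.36, 0.29

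Adjusting for both scores leaves 0.67 to 0.72 of the change-score variance, or 0.89 to 0.80 of the variance adjusted for baseline alone. An unadjusted 4-to-8 change has the same variance as baseline-to-8 under this model, so its gain is in interpretation, not precision.

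**The case against.** The strongest reply is that the two-visit schedule is consistent throughout both documents and looks deliberate. Protocol section 7 identifies MNLWHF as the instrument chosen for quality of life in these patients, and it covers every therapy state. EQ-5D-5L is ancillary, and the study is expressly unpowered. Section 6.2 speaks of measurements in general, and section 6.1.2 lists several instruments together and refers to section 10 for the schedule. All of this stands, and it limits the severity.

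Some stronger readings are tempting but are not supported:

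- *The ON-versus-OFF comparison is biased.* It is not. Baseline precedes randomisation, so baseline-to-8 change by arm is a legitimate randomised contrast. The missing week 4 score costs precision and attribution.
- *EQ-5D-5L says nothing about persistence.* The OFF week 8 score is a post-therapy value, and Protocol section 14.1.8 admits OFF subjects with 8 weeks of follow-up. What is missing is ON-arm persistence and, in OFF, a way to tell fading from no initial effect.
- *The two tests are logically contradictory.* Equality of arms lies inside the second test's null. The assumption is incompatible with that test's alternative, and the plan has no rule for choosing between them. The background on reversal concerns dilation in animals; section 7.2 leaves persistence of quality of life open.
- *The single-group test is certainly diluted.* Read literally, the analysis set contains only subjects with 8 weeks of pacing. That removes OFF subjects from the first test, and with them the dilution, but it also removes them from the second test, which needs them. The assumption sentence implies pooling, so the text is unsettled.
- *The single-group test should move to week 4.* Protocol section 5.1 expects 4 to 8 weeks before LV volume changes would be measured, and SAP section 7.9.9 allows for an effect that appears only at week 8. Protocol section 14 also calls the first phase single-arm, unblinded and open to placebo effects. With half the effect present at week 4, power is 0.38, below the worst pooled case above.

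**Conclusion.** The point holds as a gap in measurement, with low severity. The three missing scores follow directly from the schedule and need no assumption, and no analysis can recover them. The week 8 contrast by arm is sound but cannot separate 4 weeks of pacing from what follows it. The equal-effect assumption is unsupported and should go.

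The size of the dilution is conditional. It arises only if OFF subjects are pooled, with a complete 20:10 split and an effect that fades. In the extreme case the pooled mean is two thirds of the ON effect, and power is about 0.55 rather than 0.85 for an assumed 0.5 SD effect at one-sided 5%. These are illustrations for a study that claims no power.

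**What to change.** 1. In Protocol section 10.5 and Table 4, and SAP section 5.3 and Table 1, add EQ-5D-5L at the week 4 and week 12 visits, before any programming; carry this into the Protocol synopsis and visit lists.
2. Delete the equal-effect sentence from Protocol section 14.1.4 and SAP section 7.9.4, and report baseline-to-week-8 change by arm, not pooled.
3. State that the ON-versus-OFF analysis set is all randomised subjects who completed the first 4 weeks.
4. Add baseline-to-4 in all paced subjects, 4-to-8 by arm as for MNLWHF, and week 12 for persistence. These go alongside the week 8 analysis, not in its place.
5. Either schedule EQ-5D-5L at early exit or drop the rule that uses an exit score, since the visit tables do not collect one.

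The cost is an amendment to the Protocol and SAP, and a five-item form at two existing visits that already include a 21-item questionnaire. Subjects already past week 4 when the amendment takes effect would have no week 4 score. If all visits are complete, items 2 and 3 can still be done, and section 6.1.2 and its SAP counterpart (section 4.2) should say that EQ-5D-5L has one follow-up time.
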